- Concomitant treatment with DNMTi and BMS-986253 may improve treatment responses in participants with MDS by attenuating chemoattraction of myeloid derived suppressor cells to the bone marrow, indirectly disinhibiting NK- and T-cell responses against MDS stem cells, reducing neoangiogenesis, and improving cytopenia.

Objectives:

Primary objectives:

- Phase I: To determine the optimal biological dose (OBD) and RP2D of BMS-986253 with or without DNMTi (decitabine and cedazuridine) therapy in MDS participants, and to describe the safety and tolerability of BMS-986253.
- Phase II: To determine ORR to BMS-986253 with or without DNMTi (decitabine and cedazuridine) therapy in MDS, measured according to the proposed revised IWG 2018 response criteria.

Eligibility:

- Participants must have histologically or cytologically confirmed MDS according to 2016 WHO criteria[1], and

- have higher risk (HR) MDS (R-IPSS ≥ 3.5) and received a minimum of 2 and maximum of 8 cycles of DNMTi for Phase I (and a maximum of 4 cycles for Phase 2), or
- have lower risk (LR) MDS (R-IPSS <3.5) and at least one cytopenia (for both Phases I and II).
- Age ≥ 18 years
- ECOG performance status ≤ 2 (KPS $\geq 60\%$)

Design:

This study consists of two phases:

- Phase I: safety evaluation with determination of OBD of BMS-986253 with or without DNMTi (decitabine and cedazuridine), and
- Phase II: efficacy evaluation of BMS-986253 with or without DNMTi (decitabine and cedazuridine)

In both Phase I and II, participants will be enrolled into two cohorts:

- A) Higher-risk cohort (HR-MDS), including high-risk and higher intermediate-risk disease, defined as those with R-IPSS ≥ 3.5 : treatment with BMS-986253 in combination with DNMTi (decitabine and cedazuridine)
- B) Lower-risk cohort (LR-MDS), including low-risk and lower intermediate-risk disease participants, defined as those with R-IPSS <3.5 : treatment with BMS-986253 given as monotherapy

For Phase I, the safety endpoint will be DLT by D28 with the objective of defining the OBD and RP2D for BMS-986253. In addition, follow up for safety will be assessed 100 days after the end of the treatment cycle. For Phase II, the primary endpoint will be overall response rate after 6 cycles, reported separately by cohort.

TABLE OF CONTENTS

PRÉCIS.....	2
TABLE OF CONTENTS	4
STATEMENT OF COMPLIANCE	7
1 INTRODUCTION	7
1.1 Study Objectives.....	7
1.2 Background and Rationale	8
2 ELIGIBILITY ASSESSMENT AND ENROLLMENT	19

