3 STUDY IMPLEMENTATION

3.1 STUDY DESIGN

This study consists of two phases:

- Phase I: determination of OBD of BMS-986253 with and without DNMTi for HR- and LR-MDS cohorts, respectively, and
- Phase II: examining the efficacy of BMS-986253 with and without DNMTi for HR- and LR-MDS cohorts, respectively

In the Phase I, subjects will be enrolled to start treatment with BMS-986253 after a minimum of 2 cycles and up to initiation of an 8th cycle of DNMTi.

The safety endpoint will be DLT on D28. In addition, follow up for safety will be assessed 100 days after the last dose of treatment.

OBD will be the lowest tolerated dose level showing optimal biological activity, defined as maximal suppression of serum free IL-8 levels.

Participants enrolled on phase I will be treated at the corresponding BMS-986253 dose level until occurrence of disease progression, death, or unacceptable toxicity or until response assessment on C7D1 (maximum 6 cycles) if no evidence of clinical response. The participants will be followed up for overall, event- and progression-free survival until the study closure. The study will be closed when all enrolled participants have been followed up for at least 8 years or have died.

[figure not shown]
Both Phase I and II portions of study will enroll two cohorts:

A) HR-MDS: subjects with higher-risk MDS that will be treated with BMS-986253 in combination with DNMTi.

B) LR-MDS: subjects with lower-risk MDS that will be treated with BMS-986253 given as monotherapy.

In the Phase II portion, the treatment naïve subjects (or up to 4 cycles of prior DNMTi) will start treatment with BMS-986253 from the first cycle and the efficacy will be assessed until any off-treatment criteria are met (Section 3.8). BMS-986253 will be administered on days 1 and 15 of each cycle, and participants will remain on therapy until disease progression, death, or unacceptable toxicity or taken off therapy if no evidence of clinical response after 6 cycles (C7D1). The participants will be followed up for overall, event- and progression-free survival until the study closure. The study will be closed when all enrolled participants have been followed up for at least 5 years or have died.

Study treatment schema

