3.1.1 Dose Limiting Toxicity (DLT)

DLT is defined as any of the following:

- Any grade ≥ 3 non-hematologic toxicity that is possibly, probably, or definitely related to study drug, except transient (≤ 48 hour) grade 3 fatigue, nausea, local reactions, flu-like symptoms, fever, headache, infusion reactions, or laboratory abnormalities that are not associated with organ pathology.
- In the absence of active MDS, hematologic DLTs for each arm include:
 - LR-MDS arm: any grade ≥ 4 decrease in ANC or PLTs lasting more than 7 days.
 - HR-MDS arm: any grade ≥ 4 decrease ANC or PLTs lasting more than 28 days.
 - If the bone marrow at the end of cycle 1 of therapy is hypoplastic ($< 5\%$ cellularity), adjustments to treatment schedule will be allowed to delay next cycle for up to 2 weeks after count recovery or if toxicity resolves to Grade 2 or below.
- Liver Injury (DILI) as defined by a positive Hy's Law (<https://www.fda.gov/media/116737/download>):
 - AT (ALT or AST) elevation > 3 times upper limit of normal (ULN), AND
 - Total bilirubin > 2 times ULN, without initial findings of cholestasis (elevated serum alkaline phosphatase), AND
 - No other immediately apparent possible causes of AT elevation and hyperbilirubinemia, including, but not limited to, viral hepatitis, pre-existing chronic or acute liver disease, or the administration of other drug(s) known to be hepatotoxic.
- The following toxicities are not considered dose-limiting in MDS participants:
 - Grade 3 or 4 febrile neutropenia
 - Grade 3 or 4 infection only if a direct complication of cytopenias due to active underlying MDS
 - Grade 3 or 4 hypotension explained by sepsis
 - Grade 3 or 4 hemorrhage/bleeding
 - Other expected direct complication of cytopenia due to active myeloid malignancy
- Any adverse reaction that leads to dose reduction or withdrawal.

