3.1.2 Dose Escalation

Participants will receive BMS-986253 A safety lead-in will be performed. The safety lead-in will be 28 days in length and consist of 2 doses of BMS-986253 (on days 1 and 15) with a safety evaluation through day 28. Dose escalation will proceed in cohorts of 3–6 participants. The MTD is the dose level at which no more than 1 of up to 6 participants experience DLT during one cycle (28 days) of treatment, and the dose below that at which at least 2 (of ≤ 6) participants have DLT as a result of the drug. If a participant did not experience DLT and did not finish treatment, he or she will not be evaluable for toxicity and will be replaced in the dose level. Participants will be taken off treatment if unacceptable toxicity occurs and is attributed to all therapeutic

agents (see section 3.8). These patients will also be evaluated for safety and efficacy (see Section 7.4.1 and 8).

Dose Escalation Schedule	
Dose Level	Dose of BMS-986253
Level -1	600 mg IV Q2W over 60 minutes
Level 1	1200 mg IV Q2W over 60 minutes ^a
Level 2	2400 mg IV Q2W over 120 minutes ^b
Level 3	3600 mg IV Q2W over 120 minutes ^b

^a 60 minute duration will be used for pts weighing > 35 kg. For pts weighing < 35 kg the infusion duration should be 120 minutes.

^b 120 minute duration will be used for pts weighing > 35 kg. For pts weighing < 35 kg the infusion duration should be 180 minutes.

Dose escalation will follow the rules outlined in the Table below.

Number of Participants with DLT at a Given Dose Level	Escalation Decision Rule
0 out of 3	Enter up to 3 participants at the next dose level
≥ 2	Dose escalation will be stopped. This dose level will be declared the maximally administered dose (highest dose administered). Up to 3 additional participants will be entered at the next lowest dose level if only 3 participants were treated previously at that dose.
1 out of 3	Enter up to 3 more participants at this dose level. 
 • If 0 of these 3 participants experience DLT, proceed to the next dose level. • If 1 or more of this group develop DLT, then dose escalation is stopped, and this dose is declared the maximally administered dose. Up to 3 additional participants will be entered at the next lowest dose level if only 3 participants were treated previously at that dose.

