3.2.2 DNA methyltransferase inhibitors (DNMTi)

For HR-MDS cohort, the study drug of BMS-986253 will be given in combination with standard of care (SOC) FDA-approved DNMTi PO decitabine and cedazuridine according to guidelines outlined in FDA product label. SOC DNMTi will be administered via oral route once daily starting D2 of each treatment cycle through D6. [75][104][105]

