10 STATISTICAL CONSIDERATIONS

10.1 OBJECTIVES AND ENDPOINTS

OBJECTIVES	ENDPOINTS	JUSTIFICATION FOR ENDPOINTS
Primary		
Phase I: To determine OBD for BMS-986253 and RP2D, separately by cohort.	
 -Incidence of AEs, SAEs -AEs meeting protocol defined DLT criteria -AEs leading to discontinuation, death, and laboratory abnormalities. - OBD (RP2D) assessed during the first 30 days of treatment: - OBD will be the safest and lowest dose level showing optimal biological activity, defined as maximal suppression of serum free IL-8 levels.* 
*Maximal suppression of serum free IL-8 levels will be monitored for a goal of achieving IL-8 levels below the lower limit of detection of the assay in real time as outlined in Section 5.1.3.2 [ultrasensitive immunoassay based on Quanterix
	
standard endpoint for phase I protocol, see Section 3.1.1
 
Due to this being a targeted therapy, will pursue OBD instead of MTD as primary endpoint.

OBJECTIVES	ENDPOINTS	JUSTIFICATION FOR ENDPOINTS
	Simoa technology (lower limit of quantification = 0.86 pg/mL) by Myriad-RBM]	
Phase II: To determine efficacy as measured by overall response rate, separately by cohort.	-ORR per each cohort -assessed from first cycle until time of disease relapse, disease progression, or death, whichever occurs first, assessed every 3-6 months until 8 years.	Efficacy evaluation, standard for phase II protocol
Secondary		
Phase 1: To describe pharmacokinetic properties of BMS-986253 in MDS participants by cohort.	AUC, half-life, and steady state concentration Assessed during the first 30 days of treatment	Pharmacokinetic studies to evaluate for adequate absorption of therapy and define half-life/AUC and other properties of the study drug

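### HR-MDS phase I: a haematologic DLT must outlast 28 days but is assessed by day 28, and no rule counts it later or holds escalation

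*Combined protocol and SAP*

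**What the plan says.** Section 3.1.1 opens its haematologic criteria with a condition: "In the absence of active MDS, hematologic DLTs for each arm include". For HR-MDS the criterion is then a grade 4 or worse "decrease ANC or PLTs lasting more than 28 days"; for LR-MDS the same event needs to last more than 7 days.

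The time frame is given in three places:

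- Précis, Design: "the safety endpoint will be DLT by D28".
- Section 3.1: "The safety endpoint will be DLT on D28".
- Section 3.1.2: the lead-in runs 28 days "with a safety evaluation through day 28", and the MTD is defined by how many participants "experience DLT during one cycle (28 days) of treatment".

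The escalation table in Section 3.1.2 opens the next level after 0 of 3 participants with DLT, or after 1 of 3 followed by 0 of 3. It gives no window of its own and sets no condition for a cytopenia that is still open.

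**The concern.** The HR-MDS arm adds the antibody to a DNMTi. Section 14.2.2 lists fatal and serious myelosuppression among that drug's risks, and low platelets and neutrophils among its most common grade 3 or 4 laboratory abnormalities. Prolonged marrow suppression is thus a toxicity the HR criterion exists to catch.

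If the criterion can be completed only after the assessment closes, a participant with a grade 4 neutropenia or thrombocytopenia still running at D28 has no DLT on that day. With 0 of 3 recorded, the next dose level may open. The same count feeds the decision at 6 participants that fixes the OBD and recommended phase II dose (Section 3.1.2), and the DLT fraction reported at the OBD (Section 10.4.2).

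**Working it through.** **Inputs**

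- Duration threshold T: more than 28 days (HR), more than 7 days (LR); Section 3.1.1.
- End of window W: D28; précis, Sections 3.1 and 3.1.2. This agrees with the dosing: 2 doses × 14 days = 28 days.
- Cycle 1 blood counts: D1 before dosing, D8, D15 and D22, with visits allowed to move by 3 days; Section 3.4 and Section 3.6, footnote n.
- DNMTi on D2 to D6; Section 3.2.2: "SOC DNMTi will be administered via oral route once daily starting D2 of each treatment cycle through D6".

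**Formula**

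Counting both end days, an episode that starts on day d has lasted W − d + 1 days at day W. It first exceeds T on day d + T, so it completes by W only if d ≤ W − T.

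- HR: d ≤ 28 − 28 = 0. No onset on or after D1 qualifies by D28.
- LR: d ≤ 28 − 7 = 21. Onset on D1 to D21 qualifies.

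For HR, by onset day:

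| Onset | First day above 28 days | Days after D28 |
|---|---|---|
| D1 | 1 + 28 = D29 | 1 |
| D2 (first DNMTi dose) | D30 | 2 |
| D8 (first weekly count) | D36 | 8 |
| D15 (second antibody dose) | D43 | 15 |
| D22 | D50 | 22 |
| D28 | D56 | 28 |

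Counting elapsed days instead moves each date one day later, so the choice of convention does not help.

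The visit tolerance does not help either. The first scheduled count after dosing is D8, or D5 at the earliest (8 − 3). An episode first documented there passes 28 days on 5 + 28 = D33, later than a D28 visit that slips to D31 (28 + 3).

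**Is there a rule that waits or counts later?**

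- Hypoplastic marrow (3.1.1): lets the participant's own next cycle be delayed. It does not hold escalation.
- Adverse reaction leading to reduction or withdrawal (3.1.1): a separate route to a DLT. The antibody dose may not be modified (3.3). A DNMTi reduction might trigger this route; a delay would not.
- Report to the sponsor before further enrolment (3.1.2): records which criteria were met. This one will not yet have been met.
- Weekly team review (7.4.1): bases escalation on prior participants' toxicity but requires no wait.
- Bayesian monitoring (10.4.4): starts at 6 participants, so it does not act on a 0-of-3 decision.

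None of these states that an episode starting in cycle 1 and completing later is a cycle 1 DLT, or that the next level waits for it.

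**The case against.** **The escalation table names no window.** The 28 days sit in the lead-in sentence and the MTD definition, so an investigator could count an episode that completes on D36. This stands in part: the table does not forbid it. But the précis and Section 3.1 fix the endpoint at D28, and nothing requires anyone to count the event or to wait.

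**Few participants can be affected.** Haematologic DLTs count only without active MDS, while entry to this arm requires confirmed MDS with R-IPSS of at least 3.5 (Section 2.1.1). This stands. Appendix F lists CR among the disease-status options at enrolment, but a data-collection list is weak evidence that such participants will be enrolled.

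**Slow accrual gives time.** Section 10.2 expects 12 to 15 participants a year, one every 24 to 30 days (365/15 to 365/12). If they split evenly between cohorts and arrive evenly, which is an assumption, HR participants come about every 49 to 61 days. When the third reaches D28, the second is at about D77 (28 + 49) or later. Only the last participant's status would usually be open. This reduces the practical risk but does not repair the rule, and clustered enrolment would remove the protection.

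**Dose relevance.** Only the antibody dose escalates, and Section 1.2.4.1 reports no DLTs and no dose-dependent toxicities in the earlier trials. This lowers the expected harm, but phase I is there to test the combination in MDS.

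**Two stronger readings are not supported.** A reader might take the endpoint table in Section 10.1, "OBD (RP2D) assessed during the first 30 days of treatment", as a DLT window that conflicts with D28. The 30 days there belong to the OBD assessment; the DLT item is separate and has no window. A reader might also infer that the HR criterion can never be met. That is true only for onset on or after D1. An episode already present before D1 could pass 28 days by D28, although attributing it to the study drug would be hard.

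**Conclusion.** The point holds for treatment-emergent HR-MDS episodes. Every cycle 1 onset completes the criterion between D29 and D56, which is 1 to 28 days after the stated assessment. No rule counts it then or holds escalation until its status is known. Followed as written, the plan can record no DLT for an ongoing qualifying cytopenia and open the next level.

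The conclusion rests on reading the précis and Sections 3.1 and 3.1.2 together as the DLT window, and on the absence of any rule elsewhere. The reach is probably small. The documents give no rate of prolonged grade 4 cytopenia without active MDS, so no probability of wrong escalation can be stated. The LR-MDS arm is not affected in this way. An amendment is justified because a stated safety criterion and its window do not fit together, and the correction is cheap.

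**What to change.** Keep the 28-day threshold. Add to Sections 3.1.1 and 3.1.2, in substance: *For HR-MDS, a grade ≥4 ANC or platelet decrease that meets the conditions of 3.1.1 and starts on D1 to D28 is followed until it recovers or exceeds 28 days (D56 at the latest). If it exceeds 28 days it is a cycle 1 DLT. A participant unresolved at D28 has DLT status pending, and the next dose level does not open until the status is known.*

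In Sections 3.4 and 3.6, require weekly blood counts while status is pending. The extra weekly laboratory visits now stop after cycle 1. The next scheduled counts then fall at about D29, D43 and D57 (C2D1, C2D15, C3D1), too far apart to date recovery.

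**Cost.** Amendment wording, about two to four extra blood counts per affected participant, and an HR escalation delay of up to about 4 weeks. The delay arises only when such an episode is open and the other results would allow escalation.

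**Downside.** If cycle 2 starts on time, its DNMTi begins at about D30 (28 + 2) and may prolong an episode that would otherwise have recovered. The rule therefore errs toward counting a DLT and could occasionally stop escalation for a DNMTi effect.

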1.2 BACKGROUND AND RATIONALE

1.2.1 Myelodysplastic syndromes

The myelodysplastic syndromes (MDS) are a group of heterogenous clonal neoplasms of hematopoietic stem cells, characterized by dysplastic changes in at least one myeloid lineage, recurrent genetic aberrations, presence of up to 20% myeloblasts in the bone marrow, and high risk of evolution to acute myelogenous leukemia (AML).^[1] Myelodysplasia results in ineffective hematopoiesis with consequential peripheral blood cytopenia(s). Anemia is the most

common clinical presentation of MDS, but other cytopenias are also often present. Cytopenia, together with ineffective maturation of neutrophils and platelets, often result in severe and/or recurrent infections and/or bleeding episodes, respectively. In general, it is estimated that up to 1/3 of participants with MDS will die from cytopenia-related complications, up to 1/3 have disease progression into a secondary AML with poor prognosis, and the remaining 1/3 may die from causes unrelated to their MDS.[2, 3]

MDS is a disease of the elderly, with a median age at diagnosis of approximately 75 years, with ~80% of participants being ≥ 65 years.[4] Based on cancer registry data, about 10,000 new MDS cases are diagnosed per year in the United States,[5, 6] but the number is probably underestimated[7] and may be as high as $>40,000$ based on Medicare claims analyses.[8] There is a slight predominance of males.[4]

Most MDS participants (~90%) have sporadic disease and the remainder are therapy-related MDS (t-MDS), the latter often presenting in participants younger than 60 years of age. In the last decade, familial related myeloid neoplasia in persons with germ-line mutations (i.e. *RUNX1*, *GATA2*, *DDX41*, *CEPBA*, *ANKRD26*, *ETV6*) is recognized as a predisposing condition for earlier acquisition of additional MDS-related mutations and MDS development.[9] Additionally, MDS can also develop from the rare inherited bone marrow failure disorders, such as Fanconi and Diamond-Blackfan anemia, which can present in childhood and adolescence.[10]

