3.3 DOSE MODIFICATIONS

No dose modifications are allowed for BMS-986253. Dose modifications for toxicity related to the DNMTi used will be done according to standard of care per the FDA product label recommendations.

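### The DLT exemption for grade 3-4 bleeding carries no cause condition, so a possibly BMS-986253-related bleed that is not explained by MDS or the DNMTi escapes the escalation count unless the participant is withdrawn

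*Combined protocol and SAP*

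**What the plan says.** Section 3.1.1 first makes a grade 3 or higher non-hematologic toxicity a DLT when it is at least possibly related to study drug. The short list of transient exceptions attached to that rule does not mention bleeding. A later list then names toxicities that are not dose-limiting in MDS. It includes:

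- febrile neutropenia of grade 3 or 4, with no condition;
- for infection, a limit by cause: "Grade 3 or 4 infection only if a direct complication of cytopenias due to active underlying MDS";
- for low blood pressure, again a limit by cause: "Grade 3 or 4 hypotension explained by sepsis";
- for bleeding, no limit at all: "Grade 3 or 4 hemorrhage/bleeding";
- as a catch-all tied to cytopenia: "Other expected direct complication of cytopenia due to active myeloid malignancy".

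The last bullet of 3.1.1 restores DLT status to "Any adverse reaction that leads to dose reduction or withdrawal". Section 3.3 allows no dose modification of BMS-986253. For the other drug it says "Dose modifications for toxicity related to the DNMTi used will be done according to standard of care". The blood-count DLTs are introduced by "In the absence of active MDS, hematologic DLTs for each arm include" and concern neutrophil and platelet counts, not bleeds.

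The escalation table in 3.1.2 is driven by the number of participants with a DLT. Section 10.4.2 reports the fraction with a DLT at the OBD by cohort.

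**The concern.** DLT is the Phase I safety endpoint and the only event that the escalation table counts. Exempting bleeding caused by the disease is sensible: section 1.2.1 says that cytopenia and "ineffective maturation of neutrophils and platelets, often result in severe and/or recurrent infections and/or bleeding episodes". Section 14.2.2 also lists hemorrhage among the common adverse reactions of the DNMTi. Neither reason covers a bleed that the disease and the DNMTi do not explain and that the investigator thinks may be due to BMS-986253. The general rule would count that event; the exemption removes it. At stake are the decision to move to the next dose and the DLT fraction reported for the chosen dose.

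**Working it through.** No figure in the plan underlies this point, so the check is a reading of the rules followed by their effect on the table.

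**Step 1: which items carry a condition.**

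| Exempt item (3.1.1) | Cause condition in the text |
|---|---|
| Febrile neutropenia | None, but it is itself a cytopenia event |
| Infection | Complication of cytopenia from active MDS |
| Hypotension | Sepsis |
| Hemorrhage | None |
| Other complications | Cytopenia from active malignancy |

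Hemorrhage is the one item that is neither conditioned nor a cytopenia event by definition. No other section supplies a condition for it.

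**Step 2: can the uncovered event occur?** Under 2.1.1, LR-MDS entry needs only one cytopenia, and low platelets are one of three ways to qualify. Anemia or neutropenia alone is enough, so platelets may be normal. Under 2.1.2, people with ongoing or uncontrolled hemorrhagic complications are excluded. A new grade 3-4 bleed on monotherapy with normal platelets is therefore possible. A normal count does not by itself rule out the disease, because section 1.2.1 also cites poor platelet maturation. The cause has to be judged.

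**Step 3: which back-stops remain?**

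- *BMS-986253 dose reduction:* not allowed (3.3).
- *DNMTi dose reduction:* HR-MDS only, and 3.3 ties it to toxicity related to the DNMTi. For a bleed that the DNMTi does not explain, this route is essentially empty.
- *Withdrawal:* this remains, since 3.8.1 lists unacceptable toxicity and investigator discretion as removal criteria.
- *Grade 5:* outside the exemption, so a fatal bleed at least possibly related still counts.

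What escapes is a grade 3-4 bleed in a participant who stays on treatment.

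**Step 4: effect on the 3.1.2 table, with no assumed rate.** In each row, one participant has such a bleed.

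| Situation | As written | If the bleed counted |
|---|---|---|
| First 3, no other DLT | 0/3: go to next dose | 1/3: up to 3 more at this dose |
| First 3, one other participant with a DLT | 1/3: up to 3 more at this dose | 2/3: stop escalation |
| 6 treated, one other participant with a DLT | 1/6: meets the limit of at most 1 in 6 | 2/6: exceeds it |

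For the fraction in 10.4.2, one such bleed among 6 at the OBD and no other DLT would be reported as 0/6 = 0% instead of 1/6 = 16.7%.

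**The case against.** The strongest reply is that context already limits the bullet. The next item begins with the word for *other*, which places bleeding among complications of cytopenia, and febrile neutropenia is unconditional too. Bleeding is common in this disease and with the DNMTi, so a broad exemption avoids false DLTs. The uncovered event is narrow: grade 3-4 only, within 28 days, possibly drug-related, not otherwise explained, and in a participant who continues treatment.

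Much of this stands. The intent is probably as described, and the event is narrow. But the infection item in the same list states its limit explicitly, and a DLT definition should not depend on inference. Febrile neutropenia needs no condition because it is a cytopenia event; bleeding is not.

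It can also be said that the event would be seen. Section 7.4.1 bases escalation on toxicity data from earlier participants, and 3.1.2 requires a report with supporting safety data to the sponsor before further enrolment. That is correct, and the team could choose caution. The escalation table would not require it.

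A reader might go further and infer that the exemption raises the chance of escalating by some stated amount. The documents do not support that. They give no rate for drug-related bleeding in MDS. In the monotherapy trial (15 subjects), treatment-related events were all grade 1 or 2 (1.2.4.1), and the treatment-related events named in 14.1.2 include no hemorrhage term. A bound built from those lists would concern single event terms, not limited to grade 3-4 or to 28 days, in solid-tumour patients mostly on nivolumab. It would also need an assumed rate of other DLTs.

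**Conclusion.** The point holds as a narrow gap in a safeguard. The hemorrhage exemption is wider than the reason for it, and nothing elsewhere in the plan narrows it. Its size is what the table shows: one qualifying bleed in the first 3, with no other DLT, turns a 1/3 that would expand the dose level into a 0/3 that escalates. No frequency is claimed.

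This rests on reading the bullet literally and on the participant not being withdrawn. It does not mean that exempting disease-related bleeding is wrong, or that such bleeds would go unrecorded. Nor is the point extended to the toxicity pause rule in 10.4.4: its limit is set on the probability of DLT, but the pause sentence speaks of toxicities, so what it counts is not clear enough to rest a conclusion on. The weight is moderate: worth changing because DLT drives escalation and the change is small.

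**What to change.** In 3.1.1, keep the words "Grade 3 or 4 hemorrhage/bleeding" and add: *only if a direct complication of thrombocytopenia or platelet dysfunction due to active underlying MDS (or, in HR-MDS, of thrombocytopenia expected from the DNMTi)*. Leave the febrile neutropenia item as it is. Optionally add one sentence saying that the final bullet on dose reduction or withdrawal applies despite the exemption list.

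Do not add a separate clause for thrombocytopenia attributed to BMS-986253. The wording above makes it redundant, the attribution would be hard to judge, and it would sit badly with the rule that blood-count DLTs apply only without active MDS.

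The cost is one reworded bullet and, if wanted, one sentence. Blood counts are already taken weekly in Cycle 1 (3.4), so no new data are needed. The investigator must judge the cause of each bleed, as already required for infection and hypotension, and a few more events may count as DLTs.
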